## Comparing the efficacy of cardiac rehabilitation for patients with peripheral artery disease to patients with coronary artery disease/Protocol #03

### 4.7 A description of the "stopping rules" or "discontinuation criteria"

Participants can choose to withdraw from the study at any time. If the participant experiences a musculoskeletal injury during the 6-month cardiac rehabilitation program, either alternative exercises will be offered by the cardiac rehabilitation supervisor or they will be asked to discontinue the cardiac rehabilitation program until their injury heals.

### 4.8 The identification of any data to be recorded directly on the CRFs

All patients are asked during their initial visit to TRI of whether they consent to a chart review by research personnel. All participants of the study will have provided consent to a chart review and will have study data recorded on a data collection sheet with a unique research identification number.

Data to be collected includes age, biological sex, type of PAD or CAD, diabetes status, smoking status, risk factors, current exercise regimen, medications, VO2peak, HbA1c levels, total cholesterol, blood pressure, and exercise prescription.

## **5.0 Selection of Subjects**

### 5.1 Subject inclusion criteria.

Inclusion criteria will include patients over the age of 18 that have been diagnosed with lower extremity PAD or CAD. Patients with concomitant CAD and PAD will also be included in the study. Group allocation will be based on referring diagnosis. In addition, patients must be able to access and participate in the cardiac rehabilitation program at the TRI.

In order to compare patients with PAD to patients with CAD and to control for confounding variables, matching will be based on biological sex, age ( $\pm 5$  years), presence of diabetes (yes or no), smoking status (current, previous, never), and cardiac rehabilitation supervisor.

Patients diagnosed with PAD from the University Health Network and Sunnybrook Hospital will be referred by vascular surgeons to the TRI Rumsey Centre for cardiac rehabilitation. Patients with CAD referred to cardiac rehabilitation will be identified through consented chart review and invited to participate in the study.

### 5.2 Subject exclusion criteria.

Patients with vascular aneurysms, chronic heart failure, cancer, stroke, respiratory disease, or chronic kidney disease will be excluded. Patients with foot ulcers or skin breakdowns which may impede ability to exercise will also be excluded. Patients who cannot follow instructions in English will be excluded. Patients who attend less than 70% of sessions of the weekly sessions at TRI (<10 sessions in total) will be excluded from the main analysis and included in an intention-to-treat analysis.

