### **Study Agent/ Intervention/ Procedure**

The standard out-patient cardiac rehabilitation program involves weekly 1.5 hour visits at the Toronto Rehabilitation Institute Rumsey Centre for 6 months. Each visit will consist of an exercise component as well as a risk factor education lecture. Prior to the start of the program, participants will attend two assessment sessions with cardiac rehabilitation staff members to review medical history as well as complete a cardiopulmonary exercise test. During the cardiac rehabilitation program, participants will walk at 60-80% of their VO2peak heart rate based on the results of their exercise test, as per standard care procedures. Adjustments will be made to the patient's exercise prescription as their fitness improves under the discretion of the cardiac rehabilitation supervisor, as per standard care procedures. Patients will also be asked to exercise an additional four times during the week on their own time for a total of five times per week, as per standard care procedures.

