## **4.0 Study Design**

### **4.1 Primary and secondary endpoints**

Patients will undergo a baseline assessment with a laboratory technician involving a standard battery of measurements and questionnaires for characteristic purposes including anthropometrics, resting blood pressure, resting heart rate, smoking status, diabetes status, current exercise regimen, and current medications. During this assessment, clinicians will review previous and ongoing medical treatment (i.e. surgical procedures, next physician visit, ankle-brachial index measurement), presence of angina, and conduct resting 12-lead electrocardiograms. This will be followed by a medical assessment by a physician to further review medical history and safety precautions for exercise. Patients will be sent home with a walking impairment questionnaire (WIQ) (McDermott et al., 1998) and a quality of life (QOL) questionnaire (SF-36) (Brazier et al., 1992) to be submitted at their next visit. A requisition for blood work will also be given to patients to be completed prior to their second visit to determine HbA1c and total cholesterol levels.

During the second visit patients will undergo a maximal cardiopulmonary exercise test to determine cardiorespiratory fitness as measured by VO2peak and will also have an exercising 12-lead electrocardiogram. The cardiopulmonary exercise test will consist of a Bruce or modified Bruce treadmill protocol (Noonan and Dean, 2000).

After determining baseline VO2peak, an individualized walking exercise prescription will be developed by a cardiac rehabilitation supervisor which corresponds to approximately 60 to 80% of VO2peak. Patients will be invited to attend weekly 90-minute supervised exercise and education sessions at the same time every week for six months, as per standard care procedures. Patients will be encouraged to gradually increase their exercise time per session as well as frequency of sessions per week.

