### 4.4 A description of the trial treatment(s)/ intervention

The standard 6-month out-patient cardiac rehabilitation program consists of weekly 1.5 hour visits to the TRI Rumsey Centre. After determining baseline VO2peak from the exercise stress test, an individualized walking exercise prescription will be developed by a cardiac rehabilitation supervisor which corresponds to approximately 60 to 80% of the participant's VO2peak. Participants will be invited to walk around the track and attend education sessions at the same time every week for six months. Patients will be encouraged to gradually increase their exercise time walking speed. Patients will be encouraged to exercise five times a week with four sessions occurring outside of the cardiac rehabilitation program.

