## **6.0 Study Intervention**

The study intervention is consistent with the standard 6-month out-patient cardiac rehabilitation program consists of weekly 1.5 hour visits to the TRI Rumsey Centre. After determining baseline VO2peak from the exercise stress test, an individualized walking exercise prescription will be developed by a cardiac rehabilitation supervisor which corresponds to approximately 60 to 80% of the participant's VO2peak. Participants will be invited to walk around the track and attend education sessions at the same time every week for 6 months. Patients will be encouraged to gradually increase their exercise time walking speed. Patients will be encouraged to exercise five times a week with four sessions occurring outside of the cardiac rehabilitation program.

Clinicians at TRI will record distance walked, rest periods, exercising heart rate (as palpated by the radial pulse), ratings of perceived exertion (Borg scale) and rating of pain severity on the Numeric Rating Scale for Pain (numeric scale from 0 to 10, 0 being no pain and 10 being worst pain imaginable) (Hawker, Mian, Kendzerska, & French, 2011) for each exercise session at TRI. Patients will self-record their other exercise sessions on a weekly basis using exercise diaries. Frequency, time, type, exercising heart rate and rating of perceived exertion will be recorded for each exercise session outside of TRI.

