## **8.0 Statistics**

### **8.1 A description of the statistical methods to be employed**

Primary analysis to determine if patients with CAD or patients with PAD have greater improvements in  $VO_2$ peak, 6MWT, WIQ, and QOL will be tested with a series of two factor 2 (time: Baseline, End) by 2 (group: PAD, CAD) analyses of variances with Tukey's Honest Significant Difference (HSD) test for post-hoc corrections. This analysis will include patients who attended  $>70\%$  of on-site cardiac rehabilitation sessions. An intention-to-treat analysis will be conducted to include patients who attended less than 70% of the cardiac rehabilitation program sessions.

The secondary hypothesis that the magnitude of responses for patients with PAD will be dependent on biological sex will be tested through conducting a 3 factor 2 (time: Baseline, End) by 2 (group: PAD, CAD) by 2 (sex: men, women) analysis of variance. In addition to determine if the magnitude of responses are dependent on clinical presentation of PAD, a 2 factor 2 (time: Baseline, End) by 2 (type: asymptomatic, post-surgical intervention, IC) analysis of variance will be conducted.

To determine if PAD patients have greater exercising heart rate, rating of perceived exertion (Borg scale), rating of pain severity (, and training volumes than CAD patients, tertiary analysis will involve independent t-tests for these variables.

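### The attendance rule for the main analysis gives two cuts that do not match: 70% of a weekly six-month program is about 17 to 19 sessions, not 10

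*Combined protocol and SAP*

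**What the plan says.** Section 5.2, and section 2.4 in the same words, set the attendance rule: "Patients who attend less than 70% of sessions of the weekly sessions at TRI (<10 sessions in total". Patients who fall below it "will be excluded from the main analysis and included in an intention-to-treat analysis". The percentage and the session count are offered as one and the same cut.

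The program is described the same way throughout. The protocol summary has "weekly 1.5 hour visits at the Toronto Rehabilitation Institute Rumsey Centre for 6 months". Section 4.1 has "weekly 90-minute supervised exercise and education sessions at the same time every week for six months". Sections 4.4 and 6.0 agree: "The standard 6-month out-patient cardiac rehabilitation program consists of weekly 1.5 hour visits to the TRI Rumsey Centre", and patients are invited to "attend education sessions at the same time every week for 6 months". No section gives the total number of scheduled sessions.

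Section 8.1 limits the primary analysis to patients above 70% attendance on site and gives no count. It then adds: "An intention-to-treat analysis will be conducted to include patients who attended less than 70% of the cardiac rehabilitation program sessions".

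**The concern.** The rule decides who enters the analysis that section 8.1 calls primary. If the percentage and the count mark different points, that analysis has two possible populations, and the plan does not say which one applies.

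Three things are at stake.

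- **Discretion.** If the discrepancy is noticed only when the data are analysed, the choice of cut can be made with the PAD and CAD results in view.
- **The question being answered.** A minimum of about 40% attendance and a minimum of 70% describe different degrees of exposure to the program.
- **A small, matched study.** Section 8.2 recruits 28 per group in order to keep 23, a margin of 5. That margin is labelled as drop-out. Section 8.3 also takes patients with missing variables out of the main analysis, and low attenders come off the same margin. Section 5.1 matches CAD to PAD patients, so removing one member of a pair leaves the other without a match.

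**Working it through.** **Inputs**

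- Threshold: 70% of weekly on-site sessions, equated with fewer than 10 sessions (2.4, 5.2); 70% alone (8.1).
- Schedule: one session a week for six months (protocol summary, 4.1, 4.4, 6.0).
- Scheduled total N: not stated. Assumed to be 24 (6 months × 4 weeks) to 26 (half of 52 weeks), with 20 to 27 as a wider range to allow for cancelled weeks or a slightly longer calendar.
- Group size: 28 recruited, 23 required (8.2).

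**Step 1. Can the plan's figure of 10 be reproduced?** The minimum attendance is 0.70 × N, rounded up to whole sessions. Solving 0.70 × N = 10 gives N = 10 / 0.70 = 14.3. In whole sessions the minimum is 10 only for N = 13 (0.70 × 13 = 9.1) or N = 14 (0.70 × 14 = 9.8). That is about three months of weekly sessions, not six.

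**Step 2. What 70% means for this program, and what 10 sessions means**

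| Scheduled N | 0.70 × N | Minimum whole sessions | 10 / N |
|---|---|---|---|
| 20 | 14.0 | 14 | 50.0% |
| 22 | 15.4 | 16 | 45.5% |
| 24 | 16.8 | 17 | 41.7% |
| 25 | 17.5 | 18 | 40.0% |
| 26 | 18.2 | 19 | 38.5% |
| 27 | 18.9 | 19 | 37.0% |

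The figure of 10 does not appear as the minimum anywhere in the range.

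**Step 3. Could the count refer to sessions missed?** Missing 30% would be 0.30 × 24 = 7.2 to 0.30 × 26 = 7.8 sessions. That does not give 10 either.

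**Step 4. Who is classified differently?**

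- N = 24: patients attending 10 to 16 sessions, a gap of 17 − 10 = 7 sessions.
- N = 26: patients attending 10 to 18 sessions, a gap of 19 − 10 = 9 sessions.
- In attendance terms the cuts lie 70 − 41.7 = 28.3 to 70 − 38.5 = 31.5 percentage points apart.

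The count keeps these patients in the main analysis; the percentage removes them.

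**Step 5. What this means for a group.** Each three patients in the band are 3/28 = 10.7% of those recruited, or 3/23 = 13.0% of the number required.

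The plan gives no attendance distribution, so the number in the band is unknown. As an illustration only, suppose each patient attends each session independently with probability p. The share in the band is then P(10 ≤ X ≤ m − 1), where X is binomial(N, p) and m is the 70% minimum:

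- p = 0.70: 43% (N = 24) to 54% (N = 26).
- p = 0.80: 9% (N = 24) to 13% (N = 26).

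Real attendance is more clustered than this, so these figures show only that the band could hold a few patients or a large part of a group.

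**The case against.** The best defence is that the percentage is plainly the operative rule. It appears in 2.4, 5.2 and 8.1, and 8.1 is the section that specifies the analysis. The count appears only in parentheses, in one sentence used twice. On that reading the plan has one rule and a mistaken gloss. This narrows the problem correctly: the conflict lies inside the sentence in 2.4 and 5.2, and 8.1 agrees with its percentage half. It does not settle the matter. The plan never says that the percentage prevails, and a whole number of sessions is what someone checking an attendance sheet would most naturally apply.

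Other points can fairly be made.

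- **The intention-to-treat analysis brings low attenders back.** If it takes in everyone on both sides of the cut, it does not depend on the threshold and gives readers a point of comparison. That stands, but it is a separate analysis and does not define the primary one.
- **The two sets are nested.** Everyone above 70% also passes the 10-session cut, so the contrast is one of minimum attendance, not of two separate groups. That stands, and it limits how far the results could diverge.
- **The session total is inferred.** It is, but the conflict holds for every total from 20 to 27. The missing denominator is part of the defect.
- **No effect on the estimate or on power has been shown.** Correct; the plan has no data from which to show one.

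**Conclusion.** The concern holds. No plausible schedule for a weekly six-month program makes 70% equal to 10 sessions. At 24 to 26 scheduled sessions the two cuts are 7 to 9 whole sessions apart, and patients attending from about 40% to just under 70% of the program are classified differently. This rests on an inferred session total, but the conclusion does not change across 20 to 27.

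The number of patients affected, and any effect on the PAD–CAD comparison, cannot be determined from the plan. The correction should still be treated as necessary: this is the threshold that defines the primary analysis set, and a choice made after the results are known would not be credible.

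**What to change.** - State the number of scheduled on-site sessions that serves as the denominator, and say how cancelled sessions are counted.
- Choose one threshold and give its matching whole-session count. If 70% is intended, that is at least 17 of 24 or at least 19 of 26. If 10 sessions is intended, replace 70% with the matching percentage, about 40%, wherever it appears. The choice is the sponsor's.
- Use identical wording in 2.4, 5.2 and 8.1.
- In the same edit, assign a patient at exactly the threshold. Sections 2.4 and 5.2 exclude those below 70%, while 8.1 includes only those above it. This makes no difference at 24 or 26 sessions, but with 20 sessions a patient attending 14 sits exactly on the line.
- Make and date the change before any outcome data are examined by group.

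The cost is one sentence in each of three sections. No further patients, visits or measurements are needed.

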### 5.3 Withdrawal of Subjects

Participants may choose to withdraw from the study at any time. Any data collected will be discarded immediately.

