#### 3.1.1 Primary objective

The primary objective of this proposed study is to compare the magnitude of the responses to a 6-month cardiac rehabilitation program for patients with PAD in contrast to patients with CAD. The primary variable of interest will be peak oxygen consumption ( $VO_2\text{peak}$ ) with a secondary variable of interest being functional capacity, as measured by the 6-minute walk test. Tertiary variables of interest will include walking impairment, as measured by the Walking Impairment Questionnaire, and quality of life, as measured by the Short Form-36 health survey (SF-36).

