## Comparing the efficacy of cardiac rehabilitation for patients with peripheral artery disease to patients with coronary artery disease/Protocol #03

The first visit will take approximately 60 minutes and is consistent with standard care at the TRI Rumsey Centre cardiac rehabilitation program. A cardiac rehabilitation staff member will measure anthropometrics, blood pressure and will review medical history (e.g. smoking status, diabetes status, medications, current exercise regimen). The patient will also meet with a physician to review any concerns with starting the cardiac rehabilitation program. The patient will also be introduced to the study investigator if the patient expresses an interest in participating in the research study. All patients are given a blood work requisition to be completed at their local medical laboratory and if patients choose to consent to participating in the study, they will be given two questionnaires (WIQ and SF-36) to be completed for their next visit (approximately 15 minutes to complete both questionnaires).

The second visit is also consistent with standard care procedures and involves an exercise stress test with cardiac rehabilitation staff members. The exercise test will take approximately 60 minutes including preparation time, exercise time and time for questions. For the exercise stress test, patients will walk on a treadmill or pedal on a bicycle while having their breathing and blood pressure analyzed to measure VO2peak. Patients will also be attached to a 12-lead electrocardiogram to non-invasively measure activity of the heart.

The third visit will take approximately 30 minutes and will occur before the first cardiac rehabilitation class. While lying down in a private examination room, participants will have their blood pressure measured with an automated machine twice on the right arm, left arm, right ankle and left ankle in a random order. This will allow for calculation of the ankle brachial index for characteristic purposes.

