### **8.2 The number of subjects planned to be enrolled**

Sample size calculations were conducted using an alpha of 5% and a power of 0.8. Calculations were based on the primary and secondary variables of interest ( $VO_2$ peak

Comparing the efficacy of cardiac rehabilitation for patients with peripheral artery disease to patients with coronary artery disease/Protocol #03

and 6MWT distance) for PAD and CAD patients. To be conservative, the largest sample size (6MWT) was selected.

Previous literature has found that patients with PAD undergoing exercise training compared to PAD patients who did not undergo exercise training had improvements in the 6MWT of 34.9m (95 % CI 25.6–44.1 m,  $P<0.00001$ ) (Parmenter et al., 2015). In contrast, patients with CAD had improvements of  $29.6\pm12$ m following exercise training (Jaureguizar et al., 2016). Clinically significant changes have been defined as 20m for the 6MWT (Perera et al., 2006). A difference of 10 meters between groups is a conservative average between what is observed in the literature and the defined clinically significant change. The sample size calculation for a power of 0.8 would be 23 participants per group. Accounting for a 20% drop out, 28 patients with CAD and 28 patients with PAD will be recruited. Statistical significance will be set at a  $P$  value of 0.05.

A sample size of 28 participants per group is powered to detect a difference of 1.6 ml/kg/min between groups for VO2peak.

8.3 Procedure for accounting for missing, unused, and spurious data.

If data variables are missing, the whole participant data set will be excluded from the main statistical analysis. If some data is available, the participant's data will be included in the intention to treat analysis.

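### Section 8.3 drops the whole participant from the main analysis for any missing variable although each outcome has its own ANOVA, and section 5.3 leaves withdrawers no data for the ITT analysis

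*Combined protocol and SAP*

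**What the plan says.** **Missing data.** Section 8.3 states: "If data variables are missing, the whole participant data set will be excluded from the main statistical analysis". It does not say which variables count. For a participant with some data available, it adds that the "data will be included in the intention to treat analysis". No method for the missing values in that analysis is given in 8.1 or 8.3.

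**Main analysis.** Section 8.1 says that improvement in VO2peak, 6MWT, WIQ and QOL "will be tested with a series of two factor 2 (time: Baseline, End) by 2 (group: PAD, CAD) analyses of variances". Each ANOVA uses the Baseline and End values of one outcome. Section 3.1.1 ranks the outcomes: "The primary variable of interest will be peak oxygen consumption", with 6MWT second and WIQ and SF-36 third.

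**Questionnaires.** The baseline WIQ and SF-36 are filled in at home. Section 4.6 says of consenting patients that "they will be given two questionnaires (WIQ and SF-36) to be completed for their next visit"; section 4.1 describes the same arrangement.

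**Withdrawal.** Section 5.3 allows withdrawal at any time and continues: "Any data collected will be discarded immediately". It makes no exception for data gathered before withdrawal.

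**Sample size.** Section 8.2 derives 23 per group from the 6MWT, recruits 28 per group for 20% dropout, and adds: "A sample size of 28 participants per group is powered to detect a difference of 1.6 ml/kg/min".

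**The concern.** The rule in 8.3 does not fit the analysis in 8.1. An ANOVA of VO2peak needs two VO2peak values and nothing else. Read as written, 8.3 lets an unreturned questionnaire, a third-ranked outcome, take a complete pair of the primary variable out of the main analysis. Nothing is gained in return, because the ANOVAs are run separately.

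The rule in 5.3 affects the second analysis. Once a withdrawer's data are gone, 8.3 has nothing to place in the ITT analysis. The study compares two non-randomised, matched groups, so a reader will want to know whether those who withdrew from the PAD group resembled those who withdrew from the CAD group. Without their baseline characteristics that cannot be shown.

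**Working it through.** **1. The plan's own figure.** Inputs from 8.2: difference 10 m, alpha 5%, power 0.8, and SD 12 m (the CAD figure quoted there; 8.2 does not name it as the planning SD). Two-sided, n = 2 × (1.96 + 0.84)² × 12² / 10² = 22.6, so 23 per group, as stated. Then 23 × 1.2 = 27.6, so 28, as stated. After 20% dropout 28 × 0.8 = 22.4 remain.

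**2. VO2peak.** No SD is given. If the 1.6 ml/kg/min sentence means power 0.8 with 28 analysed per group, the standardised difference is 0.762 and the SD is 1.6 / 0.762 = 2.1.

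**3. Valid VO2peak pairs dropped under 8.3.** Let m be the chance that one item is missing (assumed, independent) and q the number of other items that must be present. The share of valid pairs dropped is 1 − (1 − m)^q.

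| Other items that can be missing | q | m = 2% | m = 3% | m = 5% |
|---|---|---|---|---|
| Baseline forms only, as one set | 1 | 2% | 3% | 5% |
| 6MWT and forms (as one set) at both times | 4 | 7.8% | 11.5% | 18.5% |
| 6MWT, WIQ and SF-36 separately at both times | 6 | 11.4% | 16.7% | 26.5% |
| Whole visits only | 0 | 0 | 0 | 0 |

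**4. Power at m = 3% after 20% dropout.** Two-sided t-test with n = 22.4 × 0.97^k per group, where k is the number of items that must be present. Baseline VO2peak is taken as always present, because the exercise prescription is built on it (section 4.4). Outcome by outcome, k = 2 for 6MWT (n = 21.1) and k = 1 for VO2peak (n = 21.7).

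| Rule and pattern | 6MWT power | VO2peak power |
|---|---|---|
| Outcome by outcome | 0.752 | 0.689 |
| 8.3, baseline forms only (k = 3 and k = 2) | 0.738 | 0.676 |
| 8.3, forms as one set, both times (k = 5) | 0.711 | 0.634 |
| 8.3, WIQ and SF-36 separate, both times (k = 7) | 0.683 | 0.606 |

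The first pattern costs 0.752 − 0.738 = 0.014 for 6MWT and about the same for VO2peak. The other two cost about 0.04 to 0.07 for 6MWT and 0.06 to 0.08 for VO2peak. If baseline VO2peak could also be missing (k = 8), 6MWT power would be 0.669, a fall of 0.08. If whole visits go missing, the two rules keep the same participants.

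**5. If the 20% allowance already covers incomplete participants** (the plan does not say) and nobody else is lost, n = 28 × 0.97^k. For k = 5 to 7, 6MWT power is 0.81 to 0.78 against 0.84, and VO2peak 0.73 to 0.71 against 0.79. With only the baseline forms missing, each falls by about 0.01.

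**6. Withdrawal.** Section 5.3 acts at once, so the discard precedes any use of 8.3. A participant who withdraws before month 6 has no End value and would not enter the main 2 × 2 ANOVA in any case. The effect therefore falls on the ITT analysis and on the description of withdrawers. The number affected lies between 0 and 0.2 × 56 = 11.2; the upper end would need every planned dropout to be a formal withdrawal, which nothing in the documents suggests.

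**The case against.** The case for leaving the rules alone has several sound parts.

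- **Losses may be small.** Sections 10.0 and 12.1 have investigators check forms for completeness. This should reduce missing items, but it does not change the rule and cannot complete a form that never comes back.
- **The named route costs little.** With only unreturned baseline forms at 3%, the loss is 0.03 × 22.4, under one participant per group. This stands. The larger figures need 6MWT and forms to go missing independently at both times.
- **Most of the power shortfall has another source.** With 20% dropout and no missing items, power is already 0.78 for 6MWT and 0.70 for VO2peak. A reader might blame 8.3 for the whole gap below 0.80; only the differences in step 4 belong to it.
- **Partial data are kept.** A reader might infer that measured VO2peak and 6MWT values are lost to the study. They are not: 8.3 sends them to the ITT analysis. They leave the main analysis only.
- **5.3 is narrow.** It covers people who withdraw from the study. Low attenders stay for the ITT analysis (sections 5.2 and 8.1). A reader might also infer that withdrawers vanish without trace or that 5.3 and 8.3 conflict in an unstated order. Neither follows: withdrawals can still be counted by group, and the immediate discard settles the order.
- **5.3 may reflect a commitment to participants.** The consent pages were not available, so this cannot be excluded, and any change must go through the ethics board.

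**Conclusion.** The concern holds in two limited parts. First, as written, 8.3 can remove a valid pair of the primary variable from the main analysis because an unrelated variable is missing, and 8.1 gives no reason for it. Second, 5.3 leaves withdrawers with nothing to contribute to the ITT analysis and no characteristics to compare between PAD and CAD, while leaving the main ANOVA unchanged for those who withdraw before month 6.

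The size of the first part is unknown. It runs from no loss (whole visits missing), through about 0.014 of power (baseline forms only), to about 0.04 to 0.08 (6MWT and forms missing independently at both times). These figures rest on an assumed 3% rate, 20% dropout, an SD of 12 m for 6MWT and an implied SD of 2.1 for VO2peak. The documents do not support a claim of a large loss. The defect is in the wording of the rules, does not depend on any rate, and is cheap to correct, so it should be fixed.

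**What to change.** **Section 8.3.** Let a participant enter each ANOVA for which both the Baseline and End values of that outcome exist, and report the number analysed per outcome and group. State how missing values are handled in the ITT analysis. A linear mixed model per outcome is an option, not a requirement: it helps mainly if the month-3 values in section 4.1 are used, and it lessens bias only under a missing-at-random assumption.

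**Section 5.3.** Keep data collected up to withdrawal unless the participant asks for deletion, subject to the ethics board and the consent wording, and report withdrawals by group with reasons. Keeping the data does not supply absent month-6 values; it allows withdrawers to be described and their available values to be used. If the discard rule must stay, do not describe the ITT analysis as including all enrolled participants.

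**Cost.** Protocol wording, consent wording if it repeats the discard rule, and an ethics amendment. Patient numbers will differ slightly across outcomes. No new measurement is needed.
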